Adoption	
 • Proportion reimbursed overall and on the same day as each 3HP clinic visit. • Time spent at each clinic visit. • Proportion of SMS or IVR phone call reminders delivered to participants for clinic visits or medication dosing • Proportion of SMS or IVR phone call reminders delivered to participants for missed appointments • Proportion of participants screened for active TB during DOT or refill visits • Proportion of participants screened for side effects during DOT or refill visits. 
Participants taking 3HP by SAT only
 
 • Proportion of doses confirmed using digital adherence technology. Doses directly observed (i.e., during initial or refill visits) will not be included in the denominator. • Proportion of SMS or IVR phone call reminders delivered to participants following missed doses • Proportion of weekly SMS or IVR phone call check-ins delivered to participants • Proportion of responses to weekly SMS or IVR phone call check-ins received from participants • Proportion of participants who receive appropriate follow-up (phone call or home visit) for lack of response/negative response to weekly check-in SMS or IVR phone call
Implementation	
 • Total direct and indirect patient costs related to TB preventive care services. • Self-reported patient barriers to TB preventative care services. • Patient satisfaction with TB preventive care services.

	
• Provider- and clinic-level barriers to delivery of 3HP.
Maintenance	Not applicable.

Assessment of Primary Outcome:

The primary outcome of 3HP acceptance and completion will be assessed 16 weeks after treatment initiation. According to our study definition, eligible participants who initiate and take a minimum of 11 of the 12 total 3HP doses within the 16-week time period will have met criteria for treatment acceptance and completion. Study staff will assess medication dosing using clinic records for participants taking 3HP by DOT and using a combination of 99DOTS (Everwell Health Solutions, India) digital medication adherence technology records and pill counts at refill visits for participants taking 3HP by SAT.

II. Background

Background information

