Participants randomized to the facilitated DOT arm will attend the Mulago ISS clinic on a weekly basis to ingest 3HP medication under direct observation. DOT will be defined as a designated clinic staff member observing ingestion of each dose of 3HP. Additionally, participants randomized to facilitated DOT will receive:

1. DOT cards with instructions to present directly to the pharmacy for a pharmacy-only visit, without the need to wait in the general queue.
2. Automated SMS or interactive voice response (IVR) phone call reminders at no cost to participants the day before each appointment.
3. A fixed level of reimbursement (~\$5-8/visit) for each weekly visit, conditional on either directly observed therapy or evidence of an adverse event that would preclude further treatment.

Participants who fail to return for a scheduled appointment within 24 hours will receive an SMS or IVR phone call reminder for three consecutive days after the missed appointment.

Arm 2: Facilitated SAT

Participants randomized to the facilitated SAT arm will take their first dose of medication under direct observation and be provided with a 4-week supply of 3HP to take weekly via self-administration. Participants will be asked to return to the Mulago ISS clinic after completing their 5th dose to review adherence data with the Mulago ISS clinic pharmacy technician and receive 5 additional doses of 3HP (doses 7-11). At the scheduled refill visit (dose 6) and the end-of-treatment visit (dose 12), participants will ingest 3HP doses under direct observation. Additionally, participants will receive:

1. 99DOTS-based digital adherence technology to monitor and promote adherence.
2. Weekly check-ins via two-way SMS or IVR phone call for dosing reminders and messaging asking "Are you well?" (or other similar message, as determined in our formative research phase), to serve as an alternative to weekly visits with a health worker to inquire about potential side effects
3. A fixed level of reimbursement (~\$5-8/visit) for the refill and end-of-treatment visit, conditional on either directly observed therapy or evidence of an adverse event that would preclude further treatment.

Participants who fail to return for a scheduled appointment within 24 hours will receive an SMS or IVR phone call reminder for three consecutive days after the missed appointment.

Arm 3: Patient Choice between facilitated DOT and facilitated SAT

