- Facilitated DOT participants:** After ingesting their first dose, participants will be instructed to select a date and time to attend the Mulago ISS clinic on a weekly basis. Participants will then be given a DOT card with instructions to present directly to the pharmacy for a pharmacy-only visit, without the need to wait in the general queue on their next visit date, and every visit date thereafter. Participants will be informed that they will be reimbursed at a fixed rate for weekly visits.
- Facilitated SAT participants:** After ingesting their first dose, participants will be asked to demonstrate knowledge of the appropriate dosing of 3HP, common side effects, and how to confirm dosing by making calls using the toll-free numbers. The patient will then be given sufficient pills for four doses of rifapentine and isoniazid. Participants will be asked to return to the Mulago ISS clinic at Week 6 with remaining pills (if any). Participants will be reminded that the scheduled Week 6 visit will be reimbursed at a fixed rate.

Weekly or Monthly during 3HP treatment

The following *routine* TB preventive care activities will be performed by Mulago ISS clinic staff during all 3HP DOT or refill visits:

1. **Adherence assessment:** The pharmacy technician will record in the clinic 3HP dosing register whether patients swallowed all prescribed pills including date and time of ingestion and, for patients taking 3HP by SAT, the technician will determine the number of doses taken based on 99DOTS medication adherence reports, pill counts and the participant's self-report. In addition, the pharmacy technician will receive an automated SMS when a participant does not return for a scheduled dosing visit (all participants) or does not confirm dosing by calling the toll-free number within 24 hours of a scheduled 3HP dose (Facilitated SAT participants). The technician will be encouraged to call such participants to inquire about the reason for not taking their scheduled dose and provide additional counseling as needed. Participants will be considered to have failed to complete treatment within 16 weeks if they miss 6 or more doses during 3HP treatment.
2. **Adverse events screening:**

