2. **In-depth Interviews:** will be conducted with patients to identify processes and contextual factors that influenced patient's acceptance and completion of 3HP under each delivery strategy. For each of the three delivery strategies, 24 participants (72 in total) will be purposively sampled to include those who completed all 12 doses, those who only completed the doses after being reminded for 3 days after missing the originally scheduled dose and those who failed to complete the doses despite the reminders on the day before and 3 days after the missed dose or clinic appointment. The interviews will be conducted in either English or Luganda depending on the participants' preference. The interviews will be audio recorded and later transcribed in readiness for analysis. Transcripts for interviews conducted in Luganda will be translated to English.
3. **Key Informant Interviews** will be conducted with health service providers to identify clinic-level facilitators and barriers to adoption and implementation of 3HP under each delivery strategy. Participants for the key informant interviews will be purposively sampled based on their cadres (*e.g.* Doctors, Clinical officers, Pharmacists, Pharmacy technicians, Nurses, Counselors, Peer educators and administrators) and on their involvement in the delivery of 3HP. Up to 10 providers (N=10) will be selected to take part in the key informant interviews. Key informant interviews will be conducted mainly in English by trained staff, audio-recorded and professionally transcribed.

Table 2. Participant data collection and measurements.

Procedure	Day 1	Weekly (DOT) or 6-week refill visit (SAT) during 3HP treatment (Weeks 2-11) ^a	Post-3HP treatment	
			Week 12 ^a	Every 2-3 Months (Months 3-28) ^a

Baseline questionnaire - Demographic and clinical information	X			
Survey 1 - Cost (to access clinic) - Knowledge/Beliefs/Support	X			
Survey 2^b - Reasons for choice	X			
Time-and-Motion studies^c		X		
Patient costing survey^d		X		
3HP adherence assessment		X	X	
Adverse events assessment		X	X	
Active TB assessment^e		X	X	X
3HP delivery process metrics		X		
Survey 3 - Satisfaction with care			X	
In-depth interview^f			X	

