^a 3HP treatment may last up to 16 weeks^b Patients randomized to choice arm only^c Time-and-motion studies will be performed on 40 randomly selected days (one day per week throughout the year, stratified by day of week). We anticipate that this will capture up to 250 unique participant visits per arm (750 total).^d Patient costing surveys will include 50 participants from each arm, or 150 participants total^e Only if symptomatic, except at end of follow-up.^f 24 participants/arm

Outcome Measures

Primary Outcome (Effectiveness of delivery options)

Outcome	Numerator	Denominator
Proportion accepting and completing 3HP treatment	Number who take at least 11 of 12 doses within 16 weeks of treatment initiation	Number randomized

Secondary Outcomes (Quantitative)

Outcome	Numerator	Denominator
REACH		
Treatment acceptance	Number taking at least one dose of 3HP	Number randomized
EFFECTIVENESS		
Treatment completion	Number who take at least 11 of 12 doses within 16 weeks of treatment initiation	Number taking at least one dose of 3HP

Cost-effectiveness (overall)	(Cost in Arm A – cost in Arm B) from societal perspective	(DALYs averted in Arm A – DALYs averted in Arm B) from societal perspective
Cost-effectiveness (health system)	As above, but from health system/provider perspective	As above, but from health system/provider perspective
Cost-effectiveness (patient)	As above, but from patient perspective	As above, but from patient perspective
Safety	Number for whom treatment discontinued due to adverse events or intolerance.	Number taking at least one dose of 3HP
Cumulative incidence of TB at 16 months	Number diagnosed with TB during 16-month follow-up	Risk set*
Cumulative incidence of TB at 28 months	Number diagnosed with TB during 28-month follow-up	Risk set*
ADOPTION		
All Participants		
Visit Cost Reimbursement	Number of visits for which reimbursement provided on same day	Total number of DOT/refill visits
Time to complete clinic visit	Mean and median number of minutes for each DOT/refill visit	--
SMS or IVR phone call reminders delivered	Number of SMS or IVR phone call dosing or clinic visit reminders delivered	Total number of SMS reminders scheduled to be sent
SMS or IVR phone call reminders following missed appointments	Number of SMS or IVR phone call dosing or clinic missed appointment reminders delivered	Number of participant weeks with 3HP missed appointments
Screening for active TB	Number screened for active TB during DOT visits	Total number of DOT visits

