Screening for side effects	Number screened for side effects during DOT visits	Total number of DOT visits
Participants taking 3HP by SAT only		
Dosing confirmation via 99DOTS	Number of doses recorded by 99DOTS	Total number of scheduled doses (not including doses taken during clinic visits).
SMS or IVR phone call missed dose reminders delivered	Number of SMS or IVR phone call missed dose reminders delivered	Number of participant weeks with 3HP dosing not recorded by 99DOTS
SMS or IVR phone call weekly check-in delivered	Number of weekly SMS or IVR phone call check-ins delivered	Number of participant weeks taking 3HP (not including weeks where dosing is directly observed)

Follow up (phone calls or home visits) for negative response to weekly SMS or IVR phone call check-in	Number of follow-up calls and/or home visits completed following negative response to weekly SMS or IVR phone call check-in message	Number of participant weeks of negative response to weekly SMS or IVR phone call check-in messages
IMPLEMENTATION		
Costs of preventive services	Mean total patient costs related to TB preventive care services	
Participant satisfaction	Mean score on PSQ questionnaire	--
Barriers to 3HP delivery	Thematic interpretation of provider- and clinic-level barriers to care from provider focus group discussions	
Barriers to 3HP completion	Thematic interpretation of barriers to 3HP completion from patient interviews	

* Participants will be censored at the time of active TB diagnosis or treatment initiation, death, loss to follow-up (*i.e.*, unable to be contacted and have sputum collected between 10 and 28 months after 3HP treatment discontinuation or completion), or end of the 28-month post-treatment follow-up period

Statistical Considerations

1. Primary hypotheses:

- a. The proportion who accept and complete 3HP will be highest among PLHIV randomized to the informed choice arm.
- b. The proportion of PLHIV who accept and complete 3HP can exceed 80% in a high HIV/TB burden setting.

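### Three adoption metrics in the protocol's outcome table do not match its synopsis and procedures, and the SAP does not resolve the differences (minor)

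*Protocol*

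**What the plan says.** The protocol describes the adoption metrics twice: as one-line labels in the synopsis (section I, Outcomes) and as numerators and denominators in the outcome table (section IV, Outcome Measures). SAP 2.4 refers back to the protocol for secondary outcomes. SAP 3.7 says only that each process metric is reported monthly by arm as a proportion with 95% CI, a number or a median. SAP 2.3 gives the SAP precedence, but the SAP holds no adoption definitions to apply.

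- **Check-in follow-up (SAT only).** The table counts completed calls and home visits after a negative reply, over participant-weeks with a negative reply. The synopsis line covers absent replies as well. In the procedure (Adverse events screening, Facilitated SAT) the technician is alerted by a reply of No or by 24 hours without a reply. The technician then calls up to three times, and a community health worker visits if the phone fails.
- **Missed-appointment reminders.** The numerator is "Number of SMS or IVR phone call dosing or clinic missed appointment reminders delivered" and the denominator "Number of participant weeks with 3HP missed appointments". The synopsis calls the metric "Proportion of SMS or IVR phone call reminders delivered to participants for missed appointments". Under Arms 1 and 2, a participant who misses an appointment "will receive an SMS or IVR phone call reminder for three consecutive days after the missed appointment". The row above in the table divides by "Total number of SMS reminders scheduled to be sent".
- **Screening for TB and for side effects.** Both rows stand under All Participants but name DOT visits only. The synopsis and the routine-activities list (Weekly or Monthly during 3HP treatment) name DOT or refill visits. So do the reimbursement and visit-time rows of the same table.

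**The concern.** These metrics show whether each delivery strategy was carried out as designed. Two analysts could each follow a part of the protocol and report different figures from the same data.

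The check-in row is the clearest conflict. In the SAT arm the weekly check-in replaces a weekly visit, so follow-up of participants who fall silent is a main test of delivery, and the table leaves it out. The reminder row divides reminders by weeks and reports the result as a proportion. A value above 100% would be noticed; a value below 100% would look credible while delivery was poor. The screening rows leave unclear whether SAT visits count at all.

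**Working it through.** The plan states no figure for these metrics, so there is none to reproduce. The check compares the texts and counts.

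**1. Check-in follow-up.**
- Trigger: negative reply only (table); negative or absent reply (synopsis and procedure). Every week without a reply is therefore outside the table's metric.
- Unit: the numerator counts contacts and the denominator participant-weeks. Up to 3 calls + 1 home visit = 4 contacts can follow one trigger, so the ratio can exceed 1. The table does not say whether an unanswered call counts as completed.
- Scale, 12-week course: doses 1, 6 and 12 are observed, leaving 12 − 3 = 9 check-in weeks. With 552 per arm, 9 × 552 = 4,968.
- Scale, 16-week course (Table 2, footnote a), if check-ins continue weekly: 16 − 3 = 13 weeks, and 13 × 552 = 7,176.
- Both counts assume that everyone starts. Choice-arm participants taking SAT come on top.
- Share of triggers left out = r / (a + r), where a is the rate of negative replies and r the rate of no reply. The documents give neither. Assuming a = 2–10% and r = 10–40%, the range runs from 0.10 / 0.20 = 50% to 0.40 / 0.42 = 95%.

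**2. Missed-appointment reminders.** Take one missed appointment in a participant-week, k reminders scheduled for it and a fraction d delivered. The row then reads k × d.

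| k | d | Row reads |
|---|---|---|
| 3 | 0.20 | 60% |
| 3 | 0.30 | 90% |
| 3 | 1/3 | 100% |
| 3 | 1 | 300% |
| 1 | any d | d (correct) |

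Whether reminders stop once the participant returns is not stated, so k = 3 is the upper case.

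The word dosing in the numerator is a second ambiguity. It may mean a missed dosing visit, since the adherence procedure speaks of an alert "when a participant does not return for a scheduled dosing visit (all participants". It may instead mean a missed-dose reminder, which already has its own SAT row ("Number of SMS or IVR phone call missed dose reminders delivered").

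**3. Screening rows.** SAT participants have two scheduled visits after day 1, at weeks 6 and 12. If neither is a DOT visit, the rows omit up to 2 × 552 = 1,104 SAT-arm visits at full initiation and attendance. If 25–75% of the choice arm took SAT (an assumption), add 2 × 138 = 276 to 2 × 414 = 828. If both count as DOT visits, none are omitted.

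**The case against.** Much can be said for the plan.

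- **Screening.** A reader might infer that the SAT arm has a denominator of zero. The documents do not support that as the only reading. The protocol makes SAT reimbursement at the refill and end-of-treatment visits conditional on directly observed therapy (or a treatment-precluding adverse event), and the rows sit under All Participants. Table 2 also schedules both adverse-event and active-TB assessment at week 12, although it marks process metrics only for weeks 2–11. What stands is inconsistent wording within one table.
- **Reminders.** The synopsis line gives no denominator, SAP 3.7 also allows a number, and Assessment of process metrics already plans a delivered proportion for outgoing messages and calls. A reader might infer that the row always overstates delivery threefold; it does so only if all three reminders are scheduled. What stands is that the table's ratio is not the proportion the synopsis names.
- **Check-ins.** A reader might take 4,968 weeks as a ceiling. It is not, because treatment may last 16 weeks and some choice-arm participants take SAT. The conflict over the trigger stands in full, since the synopsis and procedure name silence separately from a negative reply.

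**Conclusion.** The point holds and is minor. The follow-up row uses a narrower trigger than the synopsis and procedure and mixes contacts with participant-weeks. The reminder row reads k × d instead of d and can reach 300% at k = 3. The screening rows need one consistent visit term; whether they lose any SAT visits depends on the reading.

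The 552 per arm is the planned number, and the visit counts assume full initiation and attendance. Reply and delivery rates are not in the documents, so the number of follow-up weeks actually lost cannot be stated.

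A reader might extend this to the trial's main conclusion. That does not follow: none of these rows enters the primary outcome, the sample size or the allocation of alpha.

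**What to change.** Amend the outcome table and add a matching line to SAP 3.7.

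1. **Check-in follow-up:** participant-weeks with at least one completed call or home visit, over participant-weeks with a negative reply or no reply within 24 hours. Also show the two triggers separately. This deliberately changes the numerator from contacts to participant-weeks and keeps the ratio at or below 1.
2. **Missed-appointment reminders:** missed-appointment reminders delivered over missed-appointment reminders scheduled, naming SMS and IVR in both. Clarify or remove the word dosing. For the separate SAT missed-dose row, confirm how many reminders are scheduled per missed dose. The only hint is an interview-sampling sentence ("being reminded for 3 days after missing the originally scheduled dose"). If it is more than one, use delivered over scheduled there too.
3. **Screening:** use DOT/refill visits, including the SAT week-12 visit, in numerator and denominator of both rows, and report by arm.
4. **Synopsis:** align its units. It counts participants for screening and follow-up, where the table counts visits and participant-weeks.

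The cost is a few lines of text. Reminder delivery and check-in replies already come from the 99DOTS server, so weeks without a reply should be identifiable. Assessment of process metrics does not list screening, completed calls or home visits, so the sponsor should confirm where these are recorded. No clinical procedure has to change.

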### 3.2 Dataset assembly, cleaning and creation of new variables

Datasets will be extracted from REDCap, transferred to Stata statistical software, and re-arranged into working analytic files. At first, long format shall be used, but after cleaning and generation of relevant variables, data will be reshaped into a wide format for final analyses. Working analytic datasets will be checked, each variable at a time, for completeness, logical range, and consistency accuracy. Patient adherence data, for both directly observed and digitally confirmed doses, are stored in Everwell 99DOTS adherence database. Dosing reports extracted from the Everwell database containing detailed information on patient adherence, including date and time stamps associated with each dose taken, will be merged with trial data in order to summarize patient treatment adherence and overall treatment completion statistics.

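### The missed-dose reminder metric divides messages by weeks with no dose record, so it is not a proportion of reminders delivered and can exceed 100%

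*Protocol*

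**What the plan says.** The Synopsis (RE-AIM table, Adoption, SAT-only block) lists the metric as "Proportion of SMS or IVR phone call reminders delivered to participants following missed doses". The Outcome Measures table in protocol section IV gives its two parts:

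- Numerator: "Number of SMS or IVR phone call missed dose reminders delivered".
- Denominator: "Number of participant weeks with 3HP dosing not recorded by 99DOTS".

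Three other places in the protocol bear on these cells.

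- Adherence assessment, under the activities during treatment, says when an unconfirmed SAT dose is flagged: the pharmacy technician is alerted when a participant "does not confirm dosing by calling the toll-free number within 24 hours of a scheduled 3HP dose". This rule is written for the alert to staff. No trigger is given for the reminder to the patient.
- In-depth Interviews, under Post-3HP treatment, describes one group to be sampled as "those who only completed the doses after being reminded for 3 days after missing the originally scheduled dose". So reminders are expected to run over three days, and some doses are expected to follow them.
- The general reminder row of the same table uses a matched denominator, "Total number of SMS reminders scheduled to be sent". The weekly check-in row limits its denominator to weeks on treatment. The missed-dose row does neither.

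The SAP does not redefine the metric. Section 2.4 refers to the protocol for the full description of secondary outcomes, and section 3.7 (Adoption outcomes) plans a monthly proportion with a 95% CI for process metrics. Section 3.2 says that the dosing reports hold detailed adherence data, "including date and time stamps associated with each dose taken".

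**The concern.** A proportion of reminders delivered needs reminders due, or doses that should have triggered one, underneath. Here the top counts messages and the bottom counts weeks. This causes two problems.

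First, if more than one reminder is sent per missed dose, the ratio reflects how many messages go out per week as well as how many arrive.

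Second, the denominator has no time cut-off. If recording status is judged on the final data, a dose confirmed late, after a reminder, is no longer unrecorded. Its week leaves the denominator, and the reminder that prompted it stays in the numerator. The metric then rises when reminders work, although delivery has not changed.

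At stake is whether the trial can say that this part of facilitated SAT was delivered as intended. SAT-arm participants and those who choose SAT may differ in how often they call late, so equal delivery could look like a difference in fidelity. No formal comparison of that kind is planned, but the protocol reports adoption metrics by arm and within subgroups.

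**Working it through.** The documents give no target or expected value for this metric, so there is no stated figure to reproduce. The check works through the definition itself.

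**Inputs**

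- M: weeks with a dose missed at the reminder trigger. It cancels when no other weeks are added.
- k: reminders sent per missed week. The interview-sampling text implies up to 3 if one is sent each day (one per day is an assumption); k = 1 is the simplest case.
- d: true share of reminders delivered. Assumed.
- r: share of missed weeks recorded later by a late call. Assumed.
- s: weeks after stopping, with no reminder due, if these are counted. Assumed.

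**Formula, on the literal wording**

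metric = k·d·M / [(1 − r)·M + s]

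**Step 1: unit mismatch alone (r = 0, s = 0).** With k = 3 and d = 0.90, metric = 3 × 0.90 = 2.70. The ratio is 270% with no late call and nobody stopping.

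**Step 2: late calls alone (k = 1, s = 0).** The metric becomes d/(1 − r), which passes 100% once r > 1 − d.

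| Share later recorded (r) | d = 0.90 | d = 0.80 |
|---|---|---|
| 0 | 0.90 | 0.80 |
| 0.25 | 0.90/0.75 = 1.20 | 0.80/0.75 = 1.07 |
| 0.50 | 0.90/0.50 = 1.80 | 0.80/0.50 = 1.60 |
| 0.75 | 0.90/0.25 = 3.60 | 0.80/0.25 = 3.20 |

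In counts for the SAT arm: doses 2–5 and 7–11 are self-administered, so 552 × 9 = 4,968 doses. If 30% are unconfirmed at 24 hours, that is 1,490. One reminder delivered for 80% of them is 1,192. If half are confirmed later, 745 weeks remain unrecorded, and 1,192/745 = 1.60. The 30% affects only the counts, not the ratio.

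**Step 3: both together.** Suppose reminders stop once a dose is confirmed, so that a rescued week gets 1 reminder and an unrescued week gets 3. With d = 0.90 and r = 0.50, metric = 0.90 × (0.50 × 1 + 0.50 × 3)/0.50 = 3.60.

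**Step 4: weeks after stopping, only if they were counted (k = 1, r = 0, d = 0.90, M = 100).** With s = 50, 90/150 = 0.60. With s = 100, 90/200 = 0.45. This would pull the metric below the true 0.90.

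**Step 5: the reading under which the row works.** If unrecorded means unconfirmed at 24 hours, only on-treatment weeks count, and at most one reminder is counted per week, then r and s drop out, k = 1, and the metric returns d. None of these three conditions is in the table cells.

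**Step 6: matched denominator.** Reminders delivered over reminders scheduled gives k·d·M/(k·M) = d whatever r and s are, and cannot exceed 1.

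**The case against.** The strongest reply is that the row can be read sensibly. The Synopsis speaks of reminders after missed doses, and the only real-time rule for an unconfirmed dose is 24 hours. If the denominator is fixed at that point, no rescued week drops out. This is fair: the final-status reading is not stated, and it cannot be said that every late call removes a week. But the 24-hour rule is written for the staff alert and the cell does not refer to it, so the analyst has to choose.

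The evidence for late confirmation is also indirect. The interview-sampling text covers all three strategies and both missed doses and missed appointments. It shows that doses taken after reminders are expected, but not that they are then logged by a call. SAT doses are also established from pill counts and self-report, so some late doses may stay unrecorded in 99DOTS. The size of the late-call effect is therefore unknown.

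A reader might infer that weeks after a participant stops treatment swell the denominator, because the check-in row has an on-treatment limit and this row has none. The documents do not support that as a statement of fact. The text is silent, the block is headed as applying to people taking the regimen by SAT, and Table 2 marks process metrics only in the during-treatment column. What remains is that the limit should be written out.

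None of this removes the unit mismatch, which needs neither late calls nor stopping.

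**Conclusion.** The definition is wrong as written for one descriptive, SAT-only adoption metric. A count of messages over a count of weeks is not the proportion that the Synopsis names. It can exceed 100% on the protocol's own description of three-day reminders (270% at an assumed 90% delivery, one reminder per day). On the literal wording, late confirmation inflates it further (160% at an assumed 80% delivery, one reminder and 50% late confirmation). A binomial 95% CI does not exist for a value above 1, and in a month when every missed dose is later confirmed the literal denominator would be zero.

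The delivery, late-call and per-day reminder values are assumptions. The documents give none of them, and the true distortion could be anywhere from none (the Step 5 reading) to severalfold.

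A reader might go further and conclude that the metric measures patient behaviour rather than delivery. That is too strong: at fixed k and r the ratio still scales with the delivery rate. It is confounded by patient response, not replaced by it. The primary outcome, sample size and error rates are untouched.

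**What to change.** Redefine the row in the Outcome Measures table and repeat the definition in SAP section 3.7:

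- Denominator: scheduled self-administered doses not confirmed within 24 hours, among participants still on 3HP, whether or not confirmed later.
- Numerator: those doses with at least one reminder delivered.
- Separate line: the share of those doses confirmed later.

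An acceptable alternative is reminders delivered over reminders scheduled, as in the general reminder row. The two answer slightly different questions. With three independent attempts at 90%, message delivery is 90%, while the share of doses with at least one delivered reminder is 1 − 0.1³ = 99.9%. The plan should name the one it uses.

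The missed-appointment reminder row should be corrected at the same time. It also divides messages by participant-weeks, while the arm descriptions provide for reminders on three consecutive days after a missed appointment.

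The cost is one line per row in the table and one in the SAP, plus some data work. SAP section 3.2 confirms time stamps for doses, and the protocol's process-metrics paragraph names the 99DOTS server as the source for message delivery. The message records would still have to be linked to individual doses, which neither document describes.
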